APPENDIX E. PROTOCOL SUMMARY OF CHANGES

Protocol	Date
Version 1.0	23 August 2019
Version 2.0	13 September 2019
Version 3.0	01 February 2020
Administrative Change 1	06 March 2020
Version 4.0	29 December 2020
Version 4.1 (VHP Countries)	02 March 2021
Version 5.0	12 July 2021

The purpose of this version is to incorporate the following changes:

- Changes were made to align with the European Union/Clinical Trial Regulation to Protocol Title Page, Section 5.5, Section 5.7, Study Drug, Section 8.3 Subject Confidentiality; Operations Manual Section 3.3 Subject Information and Informed Consent, Section 1 Contacts, and Section 4.3 Reporting Adverse Events and Intercurrent Illnesses. Changes include a detailed study drug definition, description of subject confidentiality measures, and investigator reporting requirements, as well as minor updates to contact information and gender pronouns.

Rationale: To align with requirements of the EU Clinical Trial Regulation.

- Country-specific changes as required upon marketing approval of upadacitinib in Japan were made to Synopsis, Section 1, Investigational Plan; Section 4.1, Overall Study Design and Plan; Section 8.2, Ethical Conduct of the Study; Section 5.2, Contraception Recommendations, to indicate that M19-944 Study 1 and Study 2 will be changed from Phase 3 studies to post-marketing clinical studies in Japan, and conducted in compliance with the Ministerial on Good Post-marketing Study Practice (GPSP) in Japan

Rationale: Per Japan post-marketing requirements.

- Clarifications were added to Section 5.4, Allowed Therapies, to describe how peripheral joints are assessed once injected, and to specify that background medications should remain stable during the entire Remission-Withdrawal Period, including withdrawal and re-treatment phases, as applicable.

Rationale: For clarity.

- Text was revised in Section 6.2, Toxicity Management to align with current upadacitinib toxicity management standards, including updated guidance regarding MACE, malignancy, and GI perforation events, as well as abnormal laboratory values. Applicable changes were also made to Table 3 in the same section.

Rationale: For consistency with updated toxicity management guidelines based on current upadacitinib safety information.

- The following clarifications were added to Appendix D, Activity Schedule:

- Instruction to dispense at-home urine pregnancy tests at Week 104 for subjects entering the OLE in applicable countries was added to the Activity Table for Study 1 and Study 2.
- Instruction to obtain urine pregnancy tests and dispense at-home urine pregnancy tests at Week 152 for subjects entering the OLE in applicable countries was added to the Activity Table for Remission-Withdrawal Period (Prior to Retreatment).
- Instruction to administer annual TB risk assessment questionnaire, obtain annual chest x-ray and TB testing, and dispense at-home urine pregnancy tests (at RT Week 24) was added to the Activity Table for the Remission-Withdraw Period (After Retreatment).
- Removal of HBV testing at Week 122 (post baseline test for subjects from Japan only) which was too frequent beyond local requirements.

Corresponding changes were made to the applicable Individual Treatment Period Visit Activities tables in the Operations Manual.

Rationale: To correct minor errors and clarify that pregnancy monitoring and TB screening activities continue during and after Remission-Withdrawal Period.

- The text in [Appendix F](#), Open-Label Extension for Applicable Countries, was updated and expanded. Predefined time periods for participating countries were removed, and alternative guidance for end of Open-Label Extension period and final visits was added.

Rationale: For clarity and to allow continued access to upadacitinib, as needed, up to July 2025 across all applicable countries.

- eCRFs for retinal detachment and fracture were added to the list of supplemental eCRFs in the Operations Manual

Rationale: To collect detailed information about any safety events of fracture or retinal detachment.

In addition to the above modifications, this version contains the following minor changes:

- [Appendix C](#) – Updated list of protocol signatures
- The emergency medical contact was updated where applicable in Protocol and Operations Manual ([Appendix G](#)).
- Minor text edits as needed for consistency and clarity
- Correct minor clerical errors for consistency throughout the protocol

APPENDIX F. OPEN-LABEL EXTENSION FOR APPLICABLE COUNTRIES

Directions for sites in countries that require continued study drug provision to accommodate country-specific needs is found throughout this appendix. Applicable countries include but are not limited to, Belgium, Bulgaria, China, Czechia, France, Japan, Hungary, Mexico, Russia, Slovakia, Turkey, Korea, and New Zealand.

INVESTIGATIONAL PLAN

Overall Study Design and Plan (for additional details please review main Protocol)

- Subjects in Study M19-944 from both Study 1 (AS bDMARD-IR) and Study 2 (nr-axSpA) who reach Week 104 on study drug (upadacitinib 15 mg QD) will be assessed whether they are in remission, defined as achieving ASDAS (CRP) < 1.3 at Week 104 and ASDAS (CRP) < 2.1 at Week 88.
- Subjects in remission at Week 104 will be eligible for the Remission-Withdrawal Period. Subjects will be followed without study drug treatment and assessed for disease flare through Week 152. Flare is defined as an ASDAS (CRP) ≥ 2.1 at 2 consecutive visits, which are at least 2 weeks apart, or an ASDAS (CRP) > 3.5 at one visit.
 - Subjects who flare during the Remission-Withdrawal Period will receive open-label upadacitinib 15 mg QD from the time of flare for 24 weeks (re-treatment) or until the end of the Open-Label Extension period for their respective country, whichever date is later.
 - Subjects who do not flare during the Remission-Withdrawal Period, will be followed without upadacitinib treatment until Week 152 at which point they will have the option to receive open label upadacitinib for the predefined time period, if Week 152 is before the end of the Open-Label Extension period for their respective country. If Week 152 is after the end of the Open-Label Extension period, the subject will complete the study at Week 152.
- Subjects who are not in remission at Week 104 can continue to receive open-label treatment with upadacitinib 15 mg QD until the end of the Open-Label Extension period.

Subjects will be offered continued access to upadacitinib every 12 weeks until the end of the Open-Label Extension period. There are no safety or efficacy endpoints associated with the Open-Label Extension.

Following country, local (if applicable) regulatory approval, and/or applicable local reimbursement approval of the study drug in a country, or at such time that development or pursuit of regulatory approval is discontinued, subjects should be brought in for a final visit conducted in place of their regularly scheduled Open-Label Extension period study visit.

Note: These Open-Label Extension visits completed for purposes of post-Week 104 or post-Remission-Withdrawal access to upadacitinib prior to local regulatory approval/reimbursement process are considered optional and do not preclude a subject from being considered as completing the main study period (i.e., Week 104) or the Remission-Withdrawal Period.

[figure not shown]
Participating sites in applicable countries will be provided with estimated dates of when the subjects' final visits are expected to occur for planning purposes. It is acknowledged that these dates may change at any time during the course of the regulatory approval/reimbursement process. The final visit dates will be communicated to the sites based on actual approval/reimbursement dates or if decision to discontinue pursuit of regulatory approval/reimbursement is made. In the event regulatory approval, local reimbursement, or the decision to discontinue pursuit of regulatory approval/reimbursement occurs at a time point different than the estimated dates, subjects should then be brought in for their termination visit based on the actual date as provided by AbbVie. AbbVie reserves the right to terminate the study at any time.

The continued access period, also known as Open-Label Extension, is expected to end in approximately July 2025.

CONCOMITANT MEDICATION

For subjects who are not in remission at Week 104 and who receive open-label treatment with upadacitinib 15 mg QD after Week 104, addition or modification of axSpA medications can be made per Investigator judgment regardless of the disease activity status.

Figure 6. Study Schematic

Study Activities Table After Week 104 for Specified Countries Listed Above

Activity	Every 12 weeks following Week 104 or completion of Remission-Withdrawal Period/Final Visit	Unscheduled Visit	30-Day F/U Visit OR Phone Call
🗨 INTERVIEWS & QUESTIONNAIRES			
Concomitant therapy	✓	✓	✓
Review and document pregnancy avoidance recommendations with females of childbearing potential	✓	✓	✓
Latent TB risk assessment questionnaire	✓ Annually		
🩺 EXAM			
Body weight	✓	✓	
Vital signs	✓	✓	
Physical Exam	✓	✓	
AE assessment	✓	✓	✓
CXR (annually if annual TB test is newly positive [seroconversion] or a positive response to TB risk assessment questionnaire)	✓ Annually		
🧪 LOCAL LAB			
Urine pregnancy test (for all female subjects of childbearing potential)	✓		
Dispense urine pregnancy tests for monthly home testing	✓		
🧪 CENTRAL LAB			
Clinical chemistry, hematology, urinalysis	✓	✓	
HBV (post-Baseline tests for subjects from Japan only)	✓		
TB test (QuantIFERON TB Gold test [or interferon gamma release assay equivalent such as T-SPOT test] and/or local PPD skin test, if required)	✓ Annually		
💊 TREATMENT			
Dispense Study Drug	✓ (excludes Final Visit)

1.0 Introduction

The Statistical Analysis Plans (SAPs) describe the statistical analyses for the upadacitinib Study M19-944 entitled "A Phase 3 Randomized, Placebo-Controlled, Double-Blind Program to Evaluate Efficacy and Safety of Upadacitinib in Adult Subjects with Axial Spondyloarthritis Followed by a Remission-Withdrawal Period."

Study Protocol M19-944 is a global, multicenter, protocol ("master protocol") with a common screening platform for determining subject eligibility into 2 separate studies: Study 1 examines the efficacy and safety of upadacitinib in ankylosing spondylitis (AS) subjects who had an inadequate response to biologic disease-modifying antirheumatic drug therapy (bDMARD-IR). Study 2 examines the efficacy and safety of upadacitinib in non-radiographic axial spondyloarthritis (nr-axSpA) subjects.

This SAP is for the Remission-Withdrawal Period. The SAPs for Study 1 (AS, bDMARD-IR) and Study 2 (nr-axSpA) are described in separate documents.

The SAP will not be updated in case of administrative changes or amendments to the protocol unless the changes impact the analyses described in this SAP. If future protocol amendment impacts statistical analyses, this SAP will be amended accordingly. Details of SAP versions are outlined in Section [14.0](#).

Unless noted otherwise, all analyses will be performed using SAS Version 9.4 (SAS Institute Inc., Cary, NC 27513) or later under the UNIX operating system.

2.0 Study Objectives and Design

2.1 Study Objectives

[figure not shown]
Remission Withdrawal Period:

- To evaluate the maintenance of disease control after withdrawal of upadacitinib in those who achieved Ankylosing Spondylitis Disease Activity Score (ASDAS) < 1.3 at Week 104 and ASDAS < 2.1 at Week 88.

2.2 Study Design Overview

Figure 1 shows the design of Study M19-944. Remission-Withdrawal Period is illustrated in the right portion.

Figure 1. Study Schematic

AS ankylosing spondylitis; ASAS Assessment of Spondyloarthritis International Society; bDMARD IR biologic disease modifying antirheumatic drug inadequate responder; EMA European Medicines Agency; FDA Food and Drug Administration; MRI magnetic resonance imaging; nr axSpA non radiographic axial spondyloarthritis; QD once daily; SI sacroiliac; UPA upadacitinib

Subjects in Study M19-944 from both Study 1 (AS bDMARD-IR) and Study 2 (nr-axSpA) who reach Week 104 on study drug (upadacitinib 15 mg QD) will be assessed whether they are in remission, with an ASDAS (CRP) < 1.3 at Week 104 and an ASDAS (CRP) < 2.1 at Week 88.

Subjects in remission at Week 104 will be eligible for the Remission-Withdrawal Period. Subjects will be followed without study drug treatment and assessed for disease flare through Week 152. Flare is defined as an ASDAS (CRP) \geq 2.1 at 2 consecutive visits (based on observed records), which are at least 2 weeks apart, or an ASDAS (CRP) > 3.5 at one visit. Subjects who flare will receive open-label re-treatment upadacitinib

15 mg QD from the time of flare for 24 weeks (re-treatment) or longer per local country requirements. Subjects who do not flare will be followed without upadacitinib treatment until Week 152 at which point they will have the option to receive open label upadacitinib for the predefined time period, if Week 152 is before the end of the Open-Label Extension Period for their respective country. If Week 152 is after the end of the Open-Label Extension Period, the subject will complete the study at Week 152.

Efficacy analyses will be performed to characterize subject response to treatment withdrawal up to 48 weeks and response to upadacitinib re-treatment for 24 weeks respectively. Safety analyses will be performed to assess safety of reinitiated upadacitinib 15 mg QD after treatment withdrawal, including re-treatment after flare and treatment during Open-Label Extension Period after withdrawal.

An additional safety analysis will be performed to assess the totality of upadacitinib safety in the M19-944 study.

For the purposes of subject disposition and efficacy analysis, the duration of withdrawal from treatment is defined as the Withdrawal Period. The 24 weeks of exposure to treatment after flare is defined as the Re-treatment Period.

For the purposes of baseline characteristics, efficacy analysis and safety analysis, Original Baseline is defined as the value last observed prior to the first administration of study drug in the parent study, Study 1 or Study 2. The Original Baseline is used as the baseline value for all change or percent change from baseline efficacy analyses in the Withdrawal Period and for all safety summaries. For the purposes of efficacy analysis, Re-treatment Baseline is defined as the baseline value of the Re-treatment Period, which is the value last observed prior to the first administration of re-treatment study drug in the Remission-Withdrawal Period. The Re-treatment Baseline is used as the baseline value for all change or percent change from baseline efficacy analyses in the Re-treatment Period.

All analyses and summary will be performed and presented for overall (all eligible subjects) and by indication for Study 1 (bDMARD-IR AS) and Study 2 (nr-axSpA) subgroups (eligible subjects enrolled in Study 1 and Study 2, respectively).

2.3 Treatment Assignment and Blinding

Subjects will be followed without study drug treatment from Week 104 to Week 152. Subjects who flare will receive open-label upadacitinib 15 mg QD from the time of flare for 24 weeks (re-treatment) or longer per local country requirements. Subjects who do not flare will be followed without upadacitinib treatment until Week 152 at which point they will have the option to receive open label upadacitinib for the predefined time period, if Week 152 is before the end of the Open-Label Extension Period for their respective country. If Week 152 is after the end of the Open-Label Extension Period, the subject will complete the study at Week 152.

3.0 Endpoints for Remission-Withdrawal Study

3.1 Endpoints for Withdrawal Period

During the Withdrawal Period, the time-to-flare endpoint is defined as follows:

- Flare event criterion is defined as ASDAS (CRP) score > 2.1 at two consecutive visits, which are at least 2 weeks apart, or ASDAS (CRP) score > 3.5 at one visit
- Time-to-flare is defined as the number of days between the first day of treatment withdrawal and the day on which the criterion is met.

Additional endpoints during the Withdrawal Period include the following measurements assessed at scheduled time points in the Withdrawal Period:

Binary variables:

- Assessment of SpondyloArthritis international Society (ASAS) 20 response*;
- ASAS40 response*

- Bath Ankylosing Spondylitis Disease Activity Index (BASDAI) 50 response* ;
- ASAS Partial Remission (PR);
- Inactive Disease based on ASDAS(CRP) (ASDAS score < 1.3)
- Low Disease Activity based on ASDAS(CRP) (ASDAS score < 2.1);
- Major Improvement based on ASDAS(CRP) (a change from Original Baseline of ≤ 2.0);
- Clinically Important Improvement based on ASDAS(CRP) (a change from Original Baseline of ≤ 1.1);

* *Relative to Original Baseline.*

Change from Original Baseline in:

- ASDAS(CRP) and components;
- BASDAI and BASDAI components including mean of question 5 and 6 of the BASDAI (Score 0 - 10);
- Bath Ankylosing Spondylitis Functional Index (BASFI) (Score 0 - 10);
- Linear Bath Ankylosing Spondylitis Metrology Index (BASMI_{lin});
- Maastricht Ankylosing Spondylitis Enthesitis Score (MASES) for subjects with baseline enthesitis (MASES > 0);
- Patient's Assessment of Total Back Pain NRS score 0 - 10;
- Patient's Assessment of Nocturnal Back Pain NRS score 0 - 10;
- Patient's Global Assessment of Pain NRS score 0 - 10;
- Physician's Global Assessment of Disease Activity (PGA) Numeric Rating Scale (NRS) score 0 - 10;
- Patient's Global Assessment of Disease Activity (PtGA) NRS score 0 - 10;
- Tender joint count (TJC68) and swollen joint count (SJC66);
- ASAS Health Index (HI).

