
Investigational Plan:
	
Study 1 (bDMARD-IR AS) is comprised of a 35-day Screening Period; a 14-week randomized, double-blind, parallel-group, placebo-controlled period (the Double-Blind Period); a 90-week open-label, long-term extension period (the Open-Label Extension Period); and a 30-day Follow-Up Visit (F/U Visit).
 
Study 2 (nr-axSpA) is comprised of a 35-day Screening Period; a 52-week randomized, double-blind, parallel-group, placebo-controlled period (the Double-Blind Period); a 52-week open-label, long-term extension period (the Open-Label Extension Period); and a 30-day F/U Visit.

	
In the Double-Blind Period for both studies, subjects will be randomized in a 1:1 ratio to 1 of 2 treatment groups:
 
Study 1 (bDMARD-IR AS):
 
 • Group 1: upadacitinib 15 mg QD (N = 193) • Group 2: placebo QD (N = 193) 
Study 2 (nr-axSpA):
 
 • Group 1: upadacitinib 15 mg QD (N = 152) • Group 2: placebo QD (N = 152) 
Subjects in the placebo group will be switched to upadacitinib 15 mg QD at Week 14 in the Open-Label Extension Period for Study 1 (bDMARD-IR AS) and Week 52 in the Open-Label Extension Period for Study 2 (nr-axSpA).
 
Remission-Withdrawal Period:
 
 • Subjects with an ASDAS (C-reactive protein [CRP]) < 1.3 at Week 104 and an ASDAS (CRP) < 2.1 at Week 88 will be eligible for the open-label remission-withdrawal period. Subjects will be followed and assessed for potential flare through Week 152. Subjects who flare during this period (flare defined as ASDAS [CRP] ≥ 2.1 at 2 consecutive visits, which are at least 2 weeks apart, or ASDAS [CRP] > 3.5 at one visit) will be eligible to receive open-label upadacitinib 15 mg QD for 24 weeks (re-treatment) from the timepoint of flare. Subjects who do not flare through Week 152 during the withdrawal period, will have reached the end of the study. • Subjects not eligible for the withdrawal period will have reached the end of the study after the 30 day follow-up visit. 
For subjects in Japan only: Upon marketing approval of upadacitinib for the treatment of nr-axSpA in Japan, M19-944 Study 1 and Study 2 will be changed from Phase 3 studies to post-marketing clinical studies in Japan.

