8.0 Handling of Potential Intercurrent Events

For the Withdrawal Period, the potential intercurrent event is upadacitinib re-treatment. The following strategies will be used to handle the intercurrent event in efficacy analysis:

- For time-to-flare endpoint, the composite strategy will be used. Subjects who receive upadacitinib re-treatment without meeting disease flare criterion will be considered flared at the time of first dose.
- For binary endpoints, the composite strategy will be used to handle intercurrent events. Subjects who receive upadacitinib re-treatment will be considered as non-responder for all Withdrawal Period visits after first dose date.
- For continuous endpoints, the hypothetical strategy will be used to handle intercurrent events. All data after first dose date of upadacitinib re-treatment will be excluded from analysis and will be implicitly imputed by the statistical model.

For the Re-treatment Period, the potential intercurrent event is premature discontinuation of re-treatment study drug. The following strategy will be used to handle the intercurrent event in efficacy analysis:

- For all endpoints, the treatment-policy strategy will be used to handle intercurrent events. All collected efficacy data will be used as observed, regardless of whether the subject discontinued re-treatment study drug prior to the completion of the Re-treatment Period.

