9.2.1.1 Time-to-Flare

After handling of intercurrent events, for subjects without observed flare event, time-to-flare will be censored at the last available flare assessment at or prior to Week 152 visit.

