9.2.2 Efficacy Analyses in the Withdrawal Period

The distribution of event-free survival defined in Section 3.1 will be estimated using Kaplan-Meier (KM) method. Subjects who did not have flare event will be censored at the last available flare assessment visit at or prior to Week 152 visit. If a subject discontinued prior to flare or Week 152 visit, the data will be censored at the date of last flare assessment. The KM estimator for median survival time for the flare-free rate during the Withdrawal period will be provided. The corresponding 95% CI will be derived based on Greenwood's formula for variance derivation and the log-log transformation applied on the survival function. The KM plot will be provided.

Binary and continuous endpoints defined in Section 3.1 and Section 3.2 will be analyzed at scheduled time points during the Withdrawal Period.

For binary endpoints, NRI will be used for missing data handling (see Section 9.2.1.2). Descriptive statistics, including point estimate and 95% CI by normal approximation, will be provided.

For continuous endpoints, MMRM model (as described in Section 9.2.1.3) will be used based on observed data. Mean estimates with associated 95% CI will be provided. In addition, descriptive statistics based on observed data will be provided, including the number of observations, mean, and standard deviation.

Plots of efficacy endpoints by visit during the Withdrawal Period will be provided for selected endpoints.

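### SAP 3.1 sets the two-visit flare threshold at > 2.1, while SAP 2.2 and the protocol set it at ≥ 2.1, so the Kaplan-Meier event differs from the flare that triggers re-treatment

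*SAP*

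**What the plan says.** The flare rule has two limbs: a two-visit limb at 2.1 and a single-visit limb at > 3.5. The second is the same everywhere. The first is not.

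- SAP Section 3.1 (Endpoints for Withdrawal Period): "Flare event criterion is defined as ASDAS (CRP) score > 2.1 at two consecutive visits". Time to flare runs to the day this criterion is met.
- SAP Section 2.2 (Study Design Overview): "Flare is defined as an ASDAS (CRP) \geq 2.1 at 2 consecutive visits (based on observed records").
- Protocol Synopsis: "flare defined as ASDAS [CRP] ≥ 2.1 at 2 consecutive visits". Section 4.1 uses the same inclusive threshold.
- Protocol Appendix F: "Flare is defined as an ASDAS (CRP) ≥ 2.1 at 2 consecutive visits".

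The strict version is the one analysed. SAP Section 9.2.2 says: "The distribution of event-free survival defined in Section 3.1 will be estimated using Kaplan-Meier (KM) method".

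The inclusive version is the one used in conduct. According to the Synopsis, subjects who flare "will be eligible to receive open-label upadacitinib 15 mg QD for 24 weeks (re-treatment) from the timepoint of flare".

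Two further SAP rules decide what happens to a subject on the boundary. Section 8.0 says: "Subjects who receive upadacitinib re-treatment without meeting disease flare criterion will be considered flared at the time of first dose". Section 9.2.1.1 says: "for subjects without observed flare event, time-to-flare will be censored at the last available flare assessment at or prior to Week 152 visit".

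**The concern.** The SAP carries two definitions of one event, and the one tied to the Kaplan-Meier analysis is not the one that governs subject management. A programmer who follows Section 3.1 literally would code a strict inequality. A protocol-defined flare with a qualifying score of exactly 2.1 would then fail the analysis criterion.

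The strict sign also leaves a gap. SAP Section 3.1 defines low disease activity as ASDAS < 2.1, so a score of exactly 2.1 is neither low disease activity nor flare-qualifying. Under ≥ 2.1 the two states are complementary.

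The stake is the flare-free curve. The only objective of this period is maintenance of disease control after withdrawal, and time to flare is the first endpoint that SAP Section 3.1 defines. With no formal testing (SAP Sections 9.1 and 13.0), the descriptive curve is itself the result.

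**Working it through.** The plan gives no figure to reproduce. The check compares the two rules and then gauges how often they differ.

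**1. Where the rules differ.** Both rules were applied to constructed score series (not trial data) at the withdrawal visits in protocol Appendix D: Weeks 110, 116, 122, 128, 140 and 152. Criterion day = (week of the second qualifying visit − 104) × 7, for example (122 − 104) × 7 = 126.

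| ASDAS at the six visits | Flare under ≥ 2.1 | Flare under > 2.1 |
|---|---|---|
| 1.5, 2.1, 2.1, 1.9, 1.8, 1.8 | day 126 | none |
| 1.5, 2.4, 2.1, 2.0, 1.9, 1.9 | day 126 | none |
| 1.5, 1.6, 1.6, 1.8, 2.3, 2.1 | day 336 | none |
| 2.1, 2.6, 2.7, 2.8, 2.8, 2.8 | day 84 | day 126 |
| 1.5, then 2.2 throughout | day 126 | day 126 |

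The rules part only when a qualifying score equals 2.1 exactly. These are criterion dates, before SAP Section 8.0 is applied.

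**2. How often one visit reads 2.1.** The documents give no rounding rule and no ASDAS distribution after withdrawal, so normal distributions are assumed. A score stored to one decimal reads 2.1 when 2.05 ≤ X < 2.15; to two decimals, when 2.095 ≤ X < 2.105. The probability is Φ((upper − mean)/SD) − Φ((lower − mean)/SD). For mean 1.4, SD 0.6 and one decimal: Φ(1.250) − Φ(1.083) = 0.8944 − 0.8607 = 0.034.

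| Assumed mean, SD | One decimal | Two decimals |
|---|---|---|
| 1.4, 0.6 | 3.4% | 0.34% |
| 1.6, 0.7 | 4.4% | 0.44% |
| 2.0, 0.8 | 4.9% | 0.49% |
| 2.0, 0.6 | 6.5% | 0.66% |

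With more decimals the probability approaches zero.

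**3. Subject level.** Five assumed scenarios were simulated with 400,000 subjects each. Mean ASDAS rose from 1.2–1.5 to 1.6–2.5, with between-subject SD 0.3–0.6 and within-subject SD 0.3–0.5. There was no dropout, only scheduled visits were used, and the > 3.5 limb was included. Both thresholds were applied to the same scores. The table shows flare by Week 152 if nobody were re-treated:

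| Scenario | One decimal, ≥ vs > | Two decimals, ≥ vs > |
|---|---|---|
| 1 | 17.5% vs 13.2% | 15.7% vs 15.3% |
| 2 | 37.0% vs 31.4% | 34.4% vs 33.9% |
| 3 | 56.2% vs 50.5% | 53.5% vs 52.9% |
| 4 | 37.6% vs 29.2% | 33.8% vs 33.0% |
| 5 | 62.5% vs 56.4% | 59.8% vs 59.3% |

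- Strict criterion not met at the visit where ≥ 2.1 is met (met later or never): 6.2% to 16.6% of subjects at one decimal, 0.7% to 1.7% at two.
- Strict criterion never met: 4.3% to 8.4% at one decimal, 0.42% to 0.83% at two.

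**4. After SAP Section 8.0.** Re-treated subjects stay events, and only the date moves, to first dose. Event status changes only for subjects who are never re-treated and never meet the strict criterion. If 0% to 20% of them go without re-treatment (assumption), the upper bounds are:

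- one decimal: 8.4% × 0.20 = 1.7% of subjects;
- two decimals: 0.83% × 0.20 = 0.17% of subjects.

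**The case against.** **The intent is clear and the SAP largely repairs the slip.** Protocol Section 4.1 and Appendix F and SAP Sections 2.2 and 2.3 state outright that flaring subjects get re-treatment; only the Synopsis speaks of eligibility. Protocol Section 7.3 and SAP Section 8.0 both count re-treated subjects as flared. Because re-treatment starts from the time of flare, the date shift is only the delay from flare visit to first dose. The documents do not give that delay, but nothing suggests it is long beside visits 6 to 12 weeks apart. This stands and limits the size. It does not remove the problem: refusal, withdrawal or a safety reason can still leave a subject without re-treatment, and Section 8.0 would handle a protocol-defined flare as an intercurrent event.

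**The larger figures are not realistic effects.** The one-decimal results need a storage precision that no document states. The never-met percentages assume nobody is re-treated, contrary to the plan. Subjects who meet the strict rule at a later untreated visit would normally have been re-treated first. This also stands. These figures are outer limits, and the 20% is an assumption.

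**The sign may be a PDF-reading artefact.** Minus signs are missing from the improvement criteria in the same list of SAP Section 3.1. However, ≤ survives in that list and the inclusive sign survives elsewhere in the SAP, so a lost bar is possible but not shown. A look at the signed SAP would settle it.

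**No inference depends on it.** That is correct, and it is why the point is minor.

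**Conclusion.** The concern holds. As written, the event analysed under SAP Section 3.1 is not the flare defined in SAP Section 2.2 and the protocol. Section 3.1 gives no reason for the difference, and the SAP version history lists no change of threshold, so it looks like a one-symbol slip.

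Severity is minor. For most affected subjects the only consequence is an event dated at first re-treatment dose. The bounds on a change from event to censored depend on the assumed score distributions, the unstated ASDAS precision and the assumed share not re-treated. Type I error is not affected.

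**What to change.** In SAP Section 3.1, replace > 2.1 with ≥ 2.1 in the two-visit limb, and leave the > 3.5 limb as it is. Add one clause saying that the criterion is applied to ASDAS (CRP) at the precision used for the re-treatment decision, so that rounding cannot separate the two again.

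The cost is one symbol and one clause. No new data are needed and no other analysis changes. In the constructed series, the second and third columns of the first table then agree: the first two series flare on day 126, the third on day 336 and the fourth on day 84.
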